## **3.4. Examination of Subject Subgroups**

There are no prespecified subject subgroupings for analyses.

## **3.5. Multiple Comparisons**

Adjustments for multiplicity will not be made in this proof-of-concept study.

### **3.6. Missing Data and Outliers**

#### **3.6.1. Missing Data**

In general, missing data will not be imputed unless methods for handling missing data are specified. Exceptions are presented in this document. The handling of missing or incomplete dates for AE onset is described in Section 7.1.5.2 and for prior (disease-specific prior) and concomitant medications in Section 7.4.

#### **3.6.2. Outliers**

Outliers will be identified during the data management and data analysis process, but no sensitivity analyses will be conducted. All data will be included in the data analysis.

### **3.7. Data Handling Conventions and Transformations**

Only year of birth is collected in this study. Therefore, the following conventions will be used for the imputation of full date of birth:

- If year of birth is collected, “01 July” will be imputed as the day and month of birth
- If year of birth is missing, date of birth will not be imputed

In general, age collected at Day 1 (in years) will be used for analyses and presented in listings. If age at Day 1 is not available for a subject, age derived based on date of birth and the Day 1 visit date will be used instead. If a randomized/enrolled subject was not dosed with any study drug, the randomization/enrollment date will be used instead of the Day 1 visit date. For screen failures, the date the first informed consent was signed will be used for the age derivation. Age required for longitudinal and temporal calculations and analyses (eg, estimates of creatinine clearance) will be based on age derived from date of birth and the date of the measurement or event, unless otherwise specified.

Non-PK data that are continuous in nature but are less than the lower limit of quantitation (LOQ) or above the upper LOQ will be imputed as follows:

- A value that is 1 unit less than the LOQ will be used to calculate descriptive statistics if the datum is reported in the form of “< x” (where x is considered the LOQ). For example, if the values are reported as < 20 and < 2.0, values of 19 and 19.9, respectively, will be used to calculate summary statistics. An exception to this rule is any value reported as < 1 or < 0.1, etc. For values reported as < 1 or < 0.1, a value of 0.9 or 0.09, respectively, will be used to calculate summary statistics.
- A value that is 1 unit above the LOQ will be used to calculate descriptive statistics if the datum is reported in the form of “> x” (where x is considered the LOQ). Values with decimal points will follow the same logic as above.
- The LOQ will be used to calculate descriptive statistics if the datum is reported in the form of “≤ x” or “≥ x” (where x is considered the LOQ).

If methods based on the assumption that the data are normally distributed are not adequate, analyses may be performed on transformed data or nonparametric analysis methods may be used, as appropriate.

Natural logarithm transformation will be used for analyzing concentrations and PK parameters. Concentration values that are below the limit of quantitation (BLQ) will be presented as “BLQ” in the concentration data listing. Values that are BLQ will be treated as 0 at predose time points, and one-half the value of the LOQ at postdose time points for summary purposes.

The following conventions will be used for the presentation of summary and order statistics for PK concentrations:

- If at least 1 subject has a concentration value of BLQ for the time point, the minimum value will be displayed as “BLQ.”
- If more than 25% of the subjects have a concentration data value of BLQ for a given time point, the minimum and Q1 values will be displayed as “BLQ.”
- If more than 50% of the subjects have a concentration data value of BLQ for a given time point, the minimum, Q1, and median values will be displayed as “BLQ.”
- If more than 75% of the subjects have a concentration data value of BLQ for a given time point, the minimum, Q1, median, and Q3 values will be displayed as “BLQ.”
- If all subjects have concentration data values of BLQ for a given time point, all order statistics (minimum, Q1, median, Q3, and maximum) will be displayed as “BLQ.”

PK parameters that are BLQ will be imputed as one-half LOQ before log transformation or statistical model fitting.

### **3.8. Analysis Visit Windows**

#### **3.8.1. Definition of Study Day, Baseline, and Postbaseline**

Study day will be calculated from the first dose date of study drug and derived as follows:

- For postdose study days: Assessment Date – First Dosing Date + 1
- For days prior to the first dose: Assessment Date – First Dosing Date

Therefore, study day 1 is the day of first dose of study drug administration.

Baseline is defined as the last available off-treatment value collected on or prior to the first dose of study drug (ie, start time of injection).

Postbaseline is defined as any value collected after the first dose of study drug (ie, start time of injection).

Last Study Date is the latest clinic visit dates and the laboratory visit dates, including the 30-day follow-up visit date, for subjects who prematurely discontinued study or who completed study according to the Study Completion eCRF.

### 3.8.2. Analysis Visit Windows

Subject visits might not occur on protocol-specified days. Therefore, for the purpose of analysis, observations will be assigned to analysis windows.

The analysis windows for HIV-1 RNA and vital signs are provided in [Table 3-1](#).

**Table 3-1. Analysis Windows for HIV-1 RNAa and Vital Signs**

Visit ID	Nominal Day	Lower Limit	Upper Limit
Baseline		(none)	≤ Dose time on Day 1 [1] b
Day 2	2	> Dose time on Day 1 [2] b	2
Day 3	3	3	3
Day 4	4	4	5
Day 7	7	6	7
Day 8	8	8	8
Day 9	9	9	9
Day 10	10	10	11
Day 14	14	12	21
Day 29	29	22	35
Day 43	43	36	49
Day 57	57	50	70
Day 85	85	71	98
Day 113	113	99	126
Day 141	141	127	154
Day 169	169	155	182
Day 197	197	183	210
Day 225	225	211	(none)

- a The analysis window for HIV 1 RNA only applies to the change from baseline in HIV 1 RNA analysis. When defining the maximum reduction from baseline in HIV 1 RNA and percentage of subjects ever achieving HIV 1 RNA < 50 copies/mL by Day 10, all HIV 1 RNA data will be used ignoring the analysis window.
- b For vital signs as no times (only dates) were collected, Day 1 vital signs considered completed prior to administration of the dose of study drug.

The analysis windows for CD4+ cell count and CD4% are provided in [Table 3-2](#).

**Table 3-2. Analysis Windows for CD4+ and CD4%**

Visit ID	Nominal Day	Lower Limit	Upper Limit
Baseline		(none)	≤ Dose time on Day 1
Day 10	10	> Dose time on Day 1	19
Day 29	29	20	35
Day 43	43	36	49
Day 57	57	50	70
Day 85	85	71	98
Day 113	113	99	126
Day 141	141	127	154
Day 169	169	155	182
Day 197	197	183	210
Day 225	225	211	(none)

The analysis windows for hematology, chemistry (including estimated glomerular filtration rate using Cockcroft-Gault formula [eGFRCG]), and urinalysis are provided in [Table 3-3](#).

**Table 3-3. Analysis Windows for Hematology, Chemistry, Urinalysis, and eGFRCG**

Visit ID	Nominal Day	Lower Limit	Upper Limit
Baseline		(none)	≤ Dose time on Day 1
Day 3	3	> Dose time on Day 1	4
Day 7	7	5	8
Day 10	10	9	11
Day 14	14	12	21
Day 29	29	22	35
Day 43	43	36	49
Day 57	57	50	70
Day 85	85	71	98
Day 113	113	99	126
Day 141	141	127	154
Day 169	169	155	182
Day 197	197	183	210
Day 225	225	211	(none)

The analysis windows for 12-lead ECG are provided in [Table 3-4](#).

**Table 3-4. Analysis Windows for ECG**

Visit ID	Nominal Day	Lower Limit	Upper Limit
Baseline		(none)	≤ Dose time on Day 1
Day 2	2	> Dose time on Day 1	5
Day 10	10	6	19
Day 29	29	20	42
Day 57	57	43	70
Day 85	85	71	126
Day 169	169	127	196
Day 225	225	197	(none)

### 3.8.3. Selection of Data in the Event of Multiple Records in an Analysis Visit Window

Depending on the statistical analysis method, single values may be required for each analysis window. For example, change from baseline by visit usually requires a single value.

If multiple valid, nonmissing measurements exist in an analysis window, records will be chosen based on the following rules if a single value is needed:

- For baseline, the last nonmissing value on or prior to the first dose of study drug will be selected, unless specified differently. If there are multiple records with the same time or no time recorded on the same day, the baseline value will be the average of the measurements for continuous data (except for HIV-1 RNA, see below), or the measurement with the lowest severity (eg, normal will be selected over abnormal for safety ECG findings) for categorical data.
- For postbaseline values:

The record closest to the nominal day for that visit will be selected (with the exception of CD4+ cell count and CD4% in which the latest record will be selected and HIV-1 RNA level [see below]).

If there are 2 records that are equidistant from the nominal day, the later record will be selected.

If there is more than 1 record on the selected day, the average will be taken for continuous data (except for HIV-1 RNA, see below) and the worst severity will be taken for categorical data, unless otherwise specified.

- For baseline and postbaseline HIV-1 RNA, the latest (considering both date and time) record(s) in the window will be selected. If both “HIV RNA Taqman 2.0” and “HIV RNA Repeat” (ie, the HIV-1 RNA result obtained from an additional aliquot of the original sample) are available with the same collection time, the results from the “HIV RNA Repeat” will be selected for analysis purposes; otherwise, if there are multiple “HIV RNA Taqman 2.0” records with the same collection time, the geometric mean will be taken for analysis purposes.

## **4. SUBJECT DISPOSITION**

### **4.1. Subject Enrollment and Disposition**

A summary of subject enrollment will be provided by country, investigator, treatment group, and overall within Part A (all LEN and all subjects) and Part B (all TAF). The summary will present the number and percentage of subjects enrolled. For each column, the denominator for the percentage calculation will be the total number of subjects analyzed for that column.

The randomization schedule used for Part A will be provided as an appendix to the CSR.

A summary of subject disposition will present the number of subjects screened and the number of subjects who met all eligibility criteria but were not enrolled with reasons subjects not enrolled. Additional summaries of subject disposition will be provided by treatment group and overall within Part A (all LEN and all subjects) and Part B (all TAF) as well as the number and percentage of subjects in each of the categories listed below:

- All Enrolled Analysis Set
- Safety Analysis Set
- Full Analysis Set
- Completed study drug
- Did not complete study drug with reasons for premature discontinuation of study drug
- Completed study
- Did not complete the study with reasons for premature discontinuation of study

For the status of study drug and study completion and reasons for premature discontinuation, the number and percentage of subjects in each category will be provided. The denominator for the percentage calculation will be the total number of subjects in the Safety Analysis Set corresponding to that column. In addition, a flowchart will be provided to depict the disposition.

The following by-subject listings will be provided by subject ID number in ascending order to support the above summary tables:

- Reasons for premature study drug or study discontinuation (including those related to coronavirus disease 2019 [COVID-19])
- Reasons for screen failure (will be provided by screening ID number in ascending order)
- Analysis set status (indicating whether or not a subject is included in a given analysis set)

#### **4.2. Extent of Study Duration**

A subject's extent of exposure to LEN or TAF will be generated from the Study Drug Administration eCRF. Exposure data of LEN and TAF will be listed.

Due to the long-acting feature of the study drug, a summary of the extent of study duration (defined as last study day minus first dose date of study drug plus 1) will be provided, summarizing the number of subjects still in study up to each nominal visit. The total study duration will also be summarized using descriptive statistics.

B/F/TAF is provided by Sponsor with dispensing information recorded on the Accountability eCRF. Accountability data of B/F/TAF will be listed.

#### **4.3. Protocol Deviations**

Subjects who did not meet the eligibility criteria for study entry but enrolled in the study will be summarized regardless of whether they were exempted by the sponsor or not. The summary will present the number and percentage of subjects who did not meet at least 1 eligibility criterion and the number of subjects who did not meet specific criteria based on the Safety Analysis Set. A by-subject listing will be provided for those subjects who did not meet at least 1 eligibility (inclusion or exclusion) criterion. The listing will present the eligibility criterion (or criteria if more than 1 deviation) that subjects did not meet.

Protocol deviations occurring after subjects entered the study are documented during routine monitoring. The number and percentage of subjects with important protocol deviations by deviation reason and the total number of important protocol deviations by deviation reason (eg, violation of select inclusion/exclusion criteria) will be summarized by treatment group and overall for the All Enrolled Analysis Set. By-subject listings will be provided for those subjects with important protocol deviations and for those with either important protocol deviations or non-important protocol deviations related to COVID-19.

#### **4.4. Missing Protocol-Specified Information due to COVID-19**

A by-subject listing of subjects affected by the COVID-19 pandemic will be provided by subject ID number and comment visit in ascending order along with determination of if the subject missed the visit due to COVID-19 or had a virtual visit due to COVID-19.

The determination of missing or virtual visits due to COVID-19 was done using Natural Language Processing (NLP) to search the CRF comment fields. A detailed explanation of the algorithm is given in [Appendix 2](#).

## **5. BASELINE CHARACTERISTICS**

### **5.1. Demographics and Baseline Characteristics**

Subject demographic variables (ie, age, sex, race, and ethnicity) and baseline characteristics (body weight [in kg], height [in cm], body mass index [BMI; in kg/m^2]) will be summarized by treatment group and overall using descriptive statistics for continuous variables and using number and percentage of subjects for categorical variables. The summary of demographic data will be provided for the Safety Analysis Set.

A by-subject demographic and baseline characteristics listing, including the informed consent date, will be provided by subject ID number in ascending order.

### **5.2. Other Baseline Characteristics**

Other baseline characteristics include HIV-1 RNA (log10 copies/mL), CD4 cell count (/μL), CD4 percentage (%), mode of infection (HIV risk factors), HIV disease status, ever participated in pre-exposure prophylaxis (Yes/No), ever participated in post-exposure prophylaxis (Yes/No), and ART status (experienced/naïve). These baseline characteristics will be summarized by treatment group and overall using descriptive statistics for continuous variables and using number and percentage of subjects for categorical variables. The summary of these baseline characteristics will be provided for the Safety Analysis Set. No formal statistical testing is planned.

A by-subject listing of other baseline characteristics will be provided by subject ID number in ascending order.

### **5.3. Medical History**

General medical history data will be collected at screening and coded using the current version of Medical Dictionary for Regulatory Activities (MedDRA). Data on general medical history will be listed.

## **6. EFFICACY ANALYSES**

### **6.1. Primary Efficacy Endpoint**

The primary efficacy endpoint is the maximum reduction of plasma HIV-1 RNA ( $\log_{10}$  copies/mL) from Day 1 through Day 10.

Data from the placebo recipients in Cohorts 1-5 will be combined to form one placebo group. Each of the LEN treatment groups will be compared to the pooled placebo group with respect to the primary efficacy endpoint using the 2-sided t-test conducted at an alpha level of 0.05. Pairwise comparison of the maximum reduction of plasma HIV-1 RNA ( $\log_{10}$  copies/mL) from Day 1 through Day 10 among all LEN treatment groups will also be performed. The analysis will be conducted using the FAS.

### **6.2. Secondary Efficacy Endpoint**

#### **6.2.1. Number and Percentage of Subjects Ever Achieving HIV-1 RNA < 50 copies/mL by Day 10 (Part A)**

The number and percentage of subjects ever achieving HIV-1 RNA < 50 copies/mL by Day 10 will be summarized by treatment group for Part A using the FAS. Fisher exact test will be used for comparison between treatment groups.

### **6.3. Other Efficacy Endpoints**

#### **6.3.1. Definition of Other Efficacy Endpoints**

Other efficacy endpoints include:

- Change from baseline in HIV-1 RNA ( $\log_{10}$  copies/mL) by Day 10
- Number and percentage of subjects with HIV-1 RNA < 50 copies/mL
- Change from baseline in CD4 cell count (/ $\mu$ L)

#### **6.3.2. Analysis of Other Efficacy Endpoints**

Baseline values, values at each visit, and the change from baseline in HIV-1 RNA ( $\log_{10}$  copies/mL) by visit will be summarized by treatment group. Pairwise comparison of the change from baseline in HIV-1 RNA ( $\log_{10}$  copies/mL) among all treatment groups and placebo at each visit through Day 10 will be performed in the same manner as that of the primary efficacy endpoint.

Mean  $\pm$  95% confidence interval (CI) and median (Q1, Q3) of the change from baseline in HIV-1 RNA ( $\log_{10}$  copies/mL) will be plotted to Day 10 using a line plot by treatment group and visit.

Number and percentage of subjects with HIV-1 RNA < 50 copies/mL by visit will be analyzed using the missing excluded method, where missing data will be excluded in the computation of the percentages (ie, missing data points will be excluded from both numerator and denominator in the computation). The denominator for percentages at a visit is the number of subjects in the FAS with nonmissing HIV-1 RNA value at that visit. No statistical testing is planned. The number and percentage of subjects with HIV-1 RNA in the following categories will be summarized:

- < 50 copies/mL
  - < 20 copies/mL
    - < 20 copies/mL Not Detectable
    - < 20 copies/mL Detectable
  - 20 to < 50 copies/mL
- 50 to < 200 copies/mL
- 200 to < 400 copies/mL
- 400 to < 1000 copies/mL
- $\geq$  1000 copies/mL

Baseline values, values at each visit, and the change from baseline in CD4 cell count ( $\mu$ L) by visit will be summarized by treatment group. No statistical testing is planned.

All efficacy endpoints will be conducted using the FAS.

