1.6. Risk/Benefit Assessment for the Study

Potential risks associated with the study include unknown adverse events (AEs), including injection site reaction, general risks associated with frequent clinic visits and laboratory blood draws, and the associated pain and discomfort of multiple phlebotomies. Strategies to mitigate these risks include close monitoring of lab values as well as AEs. Parameters for monitoring of AEs will be well defined and closely followed.

In addition, potential risks to HIV positive subjects include prolonged exposure (weeks to months) to subtherapeutic concentrations of GS-6207, which can lead to HIV-1 developing resistance to GS-6207. Strategies to mitigate these risks include initiation of B/F/TAF, which is an FDA-approved single tablet regimen with established efficacy and safety profile, on Day 10. With the initiation of B/F/TAF most subjects are expected to achieve virologic suppression within a few weeks, which substantially reduces the risk of HIV-1 developing resistance. Similarly, subjects receiving TAF monotherapy have a risk of developing TAF resistance. However, TAF has a shorter half-life than GS-6207 and the same mitigation strategy of initiation of B/F/TAF at Day 10 will be used.

There is no direct benefit to subjects participating in this study; however, data from this study will support the development of GS-6207 and weekly TAF for the treatment of HIV-1 infection. Potential benefits may include the participant's contribution to understanding the antiviral activity, safety, tolerability, and pharmacokinetics of GS-6207 (Part A) or TAF (Part B) (i.e. how much GS-6207 or TAF gets into the blood stream).

Given the above, the benefit-risk balance for this study is considered positive.

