6.4. Early Study Discontinuation Assessments

If a subject discontinues their participation prior to Day 225, Early Termination Visit should be performed.

However, if there are any abnormal laboratory results indicating that there is a possible or probable causal relationship with the study drug, every attempt should be made to keep the subject in the study and repeat those laboratory tests weekly (or as often as deemed prudent by the Investigator) until the abnormality is resolved, returns to baseline, or is otherwise explained. If this is not possible or acceptable to the subject or investigator, the subject may be withdrawn from the study.

The following evaluations should be performed at the Early Termination Visit:

- Review of AEs and changes in concomitant medications
- Complete physical examination (urogenital/anorectal exams will be performed at the discretion of the Investigator)
- Vital signs measurement (blood pressure, pulse, respiration rate, and temperature)
- Weight
- Obtain blood and urine samples as described in Section 6.6
- Counsel subject regarding the importance of continuing a complete ARV therapy in accordance to standard of care, and refer patient to an appropriate HIV treatment facility

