6.5. Criteria for Discontinuation of Study

Study may be discontinued in the following instances:

- Intercurrent illness that would, in the judgment of the investigator, affect assessments of clinical status to a significant degree. Following resolution of intercurrent illness, the subject may resume study dosing at the discretion of the investigator.
- Unacceptable toxicity, or toxicity that, in the judgment of the investigator, compromises the ability to continue study-specific procedures or is considered to not be in the subject's best interest
- Subject request to discontinue for any reason
- Subject noncompliance with B/F/TAF
- Pregnancy during the study; refer to [Appendix 6](#) and [Appendix 7](#)
- Discontinuation of the study at the request of Gilead, a regulatory agency or an institutional review board or independent ethics committee (IRB/IEC)

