- d Within 72 hours of permanently discontinuing study. Counsel subject regarding the importance of continuing a complete ARV therapy in accordance to standard of care, and refer patient to an appropriate HIV treatment facility.
- e Females of childbearing potential only
- f Hematology: CBC with differential and platelet count
- g Chemistries: Alkaline phosphatase, AST, ALT, GGT, total bilirubin, direct and indirect bilirubin, total protein, albumin, LDH, CPK, bicarbonate, BUN, calcium, chloride, creatinine, glucose, phosphorus, magnesium, potassium, sodium, uric acid, and amylase (reflex lipase testing if total amylase > 1.5 × ULN).
- h Fasting overnight (≥ 6 hours) required for Days 1, 3, 7, 10, 85, 169 and 225

- i FSH test is required for female subjects who have stopped menstruating for ≥ 12 months but do not have documentation of ovarian hormonal failure.
- j Vital signs – blood pressure, pulse, respiration rate, and temperature, weight
- k Urinalysis and Urine Chemistry: including color & clarity, specific gravity, pH, glucose, ketones, bilirubin, urobilinogen, blood, nitrite, leukocyte esterase and microscopic (if microscopic elements are seen), urine protein, albumin, creatinine, phosphate, calcium, magnesium and uric acid
- l Part A: Serial blood samples to determine pharmacokinetics (PK) in plasma will be collected at the following time points relative to study drug dosing 0 (pre-dose), 1, 2, 4, 8, 12 and 24 hours post dose.
[REDACTED]
- n Part A: Single Anytime PK sample to be collected at the Day 3, 4, and 7 through 225 visits.
- o Part B: Plasma PK samples to be collected at the following time points relative to study drug dosing: 0 (pre-dose), 0.5, 1, 2, 3, 4, 6, 8, 10, 12, 24 and 48 hours post dose; as well as at Days 4, [REDACTED] 7, 8, 9 and 10 at approximately the same time in the morning as pre-dose on Day 1.
- p Part B: PBMC PK samples to be collected at the following time points relative to study drug dosing: 0 (pre-dose), 1, 2, 4, 6, 8, 12, 24 and 48 hours post dose, as well as at Days 4, [REDACTED], 7, 8, 9 and 10 at approximately the same time in the morning as pre-dose on Day 1.
[REDACTED]
- r Part A: subjects require the HIV-1 capsid genotype/phenotype to confirm eligibility prior to randomization. Part B: the capsid genotype/phenotype will be completed for informational purposes, but it is not be required to confirm eligibility.

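### The by-visit percentage with HIV-1 RNA < 50 copies/mL uses only the missing-excluded method and may be overstated after Day 10 if participants who leave are suppressed less often than those who stay

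*SAP*

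**What the plan says.** SAP 6.3.2 analyses the share of participants below 50 copies/mL at each visit by the missing-excluded method: "missing data points will be excluded from both numerator and denominator in the computation". It then fixes the denominator: "The denominator for percentages at a visit is the number of subjects in the FAS with nonmissing HIV-1 RNA value at that visit". The viral-load categories listed there have no row for participants without a value. For this summary, "No statistical testing is planned". SAP 3.6.1 supplies no fallback, since "missing data will not be imputed unless methods for handling missing data are specified". No missing-as-failure or other sensitivity version of the table is described.

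Protocol 6.5 includes "Subject noncompliance with B/F/TAF" among the reasons for which the study may be discontinued. For anyone leaving before Day 225, protocol 6.4 says an "Early Termination Visit should be performed", and the footnote in protocol Appendix 2 times it "Within 72 hours of permanently discontinuing study". Plasma HIV-1 RNA is on that visit's schedule. Under protocol 5.5, a Part A participant who stops B/F/TAF can switch regimen, subject to a list of prohibited agents.

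SAP 3.2 adds a column for all Part A participants to this table.

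**The concern.** The planned percentage answers how many of those with a value at the visit are suppressed. A reader will often take it as the share of dosed participants who are suppressed. The two agree only if participants without a value are suppressed as often as those with one.

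The plan gives reason to doubt that. A participant discontinued for not taking B/F/TAF is more likely than average to be viraemic, and disappears from every later denominator. The displayed percentage can then rise because someone did badly and left. In dose groups of 6 or 8 a single person moves it visibly, and there is no test or alternative calculation to alert the reader.

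Suppression after Day 10 bears on the protocol's risk discussion (section 1.6): "With the initiation of B/F/TAF most subjects are expected to achieve virologic suppression within a few weeks". That expectation concerns everyone who starts B/F/TAF, not only those still attending.

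**Working it through.** **Inputs.** Planned group sizes are 6 per GS-6207 dose, 10 pooled placebo and 8 per TAF dose (protocol 8.8, SAP 1.3), and up to 40 in the Part A total column (SAP 3.2). The visit windows are in SAP Table 3-1. The documents state no dropout rate, so the numbers of leavers below are assumptions.

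**The plan's own figure.** No figure is stated for this endpoint. The only stated figure that uses these group sizes is the 99% power for the primary endpoint, and it reproduces: above 0.9999 for 6 versus 10 (difference 2.79, SD 0.526) and 0.9997 for 8 versus 10 (difference 1.43, SD 0.52). This confirms the group sizes and says nothing about the by-visit table.

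**What the Early Termination value covers.** Suppose a participant leaves and has the termination sample on Day 100. It falls in the Day 113 window (Days 99 to 126). The participant then has no value at Days 141, 169, 197 and 225. Only a value on Day 211 or later counts at Day 225.

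**Size.** Let n be the FAS participants in the group, d those who left and have no value at the visit, and s those observed below 50, with nobody else missing.

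- Missing-excluded: s/(n − d)
- Leavers counted as not below 50: s/n
- Gap: s/(n − d) − s/n = [s/(n − d)] × (d/n)

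With everyone observed suppressed (s = n − d):

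| Group | n | One leaver: excluded / counted as failure | Gap (points) | Two leavers: excluded / counted as failure | Gap (points) |
|---|---|---|---|---|---|
| GS-6207 dose | 6 | 5/5 = 100% / 5/6 = 83.3% | 16.7 | 4/4 = 100% / 4/6 = 66.7% | 33.3 |
| TAF dose | 8 | 7/7 = 100% / 7/8 = 87.5% | 12.5 | 6/6 = 100% / 6/8 = 75.0% | 25.0 |
| Pooled placebo | 10 | 9/9 = 100% / 9/10 = 90.0% | 10.0 | 8/8 = 100% / 8/10 = 80.0% | 20.0 |
| Part A total | 40 | 39/39 = 100% / 39/40 = 97.5% | 2.5 | 38/38 = 100% / 38/40 = 95.0% | 5.0 |

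**Direction.** Let p = s/(n − d) be the planned figure and q the share of leavers who are in fact below 50. The full-group value is (s + qd)/n, so p minus that value equals (d/n)(p − q). The planned figure is too high only when q < p. Take n = 6, one leaver and one observed value of 50 or more. Then p = 4/5 = 80.0%, and the full-group value is 4/6 = 66.7% if the leaver is viraemic or 5/6 = 83.3% if suppressed. The planned figure is 13.3 points too high in the first case and 3.3 points too low in the second.

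**Visits missed by participants still in the study.** With n = 6, one COVID-19 miss and the other five suppressed, missing-excluded gives 5/5 = 100%. Counting every absence as failure gives 5/6 = 83.3%, although nobody has left or failed. If only discontinuations count as failures, the formula is s/(n − k), where k is the number who missed the visit but remain in the study. Here that gives 5/5 = 100%, as it should.

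**The case against.** The strongest reply is that this is an untested, descriptive item among the SAP's other efficacy endpoints, about a background regimen that everyone receives. No dose comparison depends on it. Attrition is reported elsewhere: SAP 4.1 gives discontinuation reasons by treatment group, SAP 4.2 the number still in the study at each nominal visit, and SAP 4.4 lists COVID-19 missed visits. The table gives counts as well as percentages, and with 6 to 10 people per group a reader can reconcile 5/5 with 5/6. Noncompliance is a ground on which discontinuation may occur, not a mandatory exit. The Early Termination sample can capture a viraemic value, and the Part A switch rule lets some participants stay and keep contributing. All of this stands. It narrows the problem and lowers its weight, but supplies no value for later windows and leaves the reader to rebuild the percentage from separate outputs.

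Three stronger readings are tempting, and the documents do not support them.

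- *Suppression is overstated.* The direction depends on why values are missing, and the documents give neither a dropout rate nor the virologic status of leavers.
- *This table is the planned evidence that resistance is mitigated.* No section says so. Protocol 1.6 rests on the established efficacy of B/F/TAF, and emergent resistance has its own secondary endpoints.
- *The two below-50 endpoints are handled inconsistently.* The Day 10 endpoint asks whether a participant was ever below 50 and ignores visit windows (SAP Table 3-1, footnote a). A by-visit percentage needs a value at each visit. These are different quantities.

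A further objection also stands: making missing-as-failure the headline would replace one untestable assumption with another. A suppressed leaver would then lower the percentage as much as a true failure does.

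**Conclusion.** The point holds in a conditional form. After Day 10 the by-visit percentage may be overstated, and the SAP plans nothing beside it that shows by how much. With nobody else missing and all others suppressed, one viraemic leaver is worth 16.7 points in a group of 6, 12.5 in a group of 8, 10.0 in pooled placebo and 2.5 in the Part A total. These sizes assume that the leaver is viraemic and has no value in the window. If leavers are suppressed as often as stayers there is no bias, and if more often, the planned figure is slightly low.

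This is a cheap improvement to a descriptive table. It does not threaten the trial's conclusions: the primary endpoint and the ever-below-50-by-Day-10 endpoint do not use this rule. Nor does it support replacing the planned percentage.

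**What to change.** In SAP 6.3.2, keep missing-excluded as the planned figure. For visits after Day 10, add the following to the same table:

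1. A sensitivity percentage in which windows after premature study discontinuation that hold no value count as not < 50 copies/mL. A window with an observed value, including an Early Termination value, uses that value. Visits missed by participants still in the study, including COVID-19 misses identified under SAP 4.4, stay excluded.
2. The number with a value over the number in the FAS (n/N) at each visit.
3. A no-virologic-data row, split into discontinued, missed because of COVID-19 and missed for other reasons.

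The cost is SAP wording and one extra table from data already collected, with no protocol amendment. If the SAP is already final, the addition can be documented in the CSR, as SAP section 1 provides for later changes. The downside is that the sensitivity figure is conservative: a participant who left while suppressed counts as a failure, worth up to 17 points in a group of 6 with nobody else missing. The two percentages should therefore be presented as a range. They span the cases from no leaver suppressed to leavers suppressed as often as stayers.
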